This study aims to understand the impact of intervention on the functional fitness and quality of life of elderly participants befor and after the intervention. The assessment tools used include functional fitness tests and a quality of life questionnaire, along with the collection of basic participant information. Both groups underwent pre-tests befor the intervention, which included a fall risk assessment, functional fitness assessment, and quality of life satisfaction survey. After completing the 12-week, 36-session intervention, post-tests were conducted to measure the effectiveness of the intervention.

1. Basic Participant Information:

Includes gender, age, exercise habits, self-perceived health status questionnaire, and Body Mass Index (BMI).

2. Functional Fitness Tests:

(a) Chair Stand Test:

Measures lower body strength/endurance.

Participants sit in a chair without armrests and stand up as many times as possible within 30 seconds.

(b) Chair Sit and Reach Test:

Assesses lower body flexibility.

Participants sit on the edge of a chair with one knee bent at 90 degrees and try to reach their toes with their hands. The distance between the fingertips and toes is measured.

(c) 8-Foot Up-and-Go Test:

Evaluates agility and dynamic balance.

Participants sit in a chair, stand up upon hearing a signal, walk around a designated point 8 feet away, and return to the chair. The time taken to complete the task is recorded.

(d) 2-Minute Walk Test:

Measures aerobic endurance.

Participants walk in place for 2 minutes, and the number of times the knees are lifted to a specific height is counted.

3. Quality of Life Questionnaire:

Administered using the "Taiwanese version of the World Health

Organization Quality of Life Questionnaire-Brief Form

(WHOQOL-BREF Taiwanese version)."

Consists of 28 questions divided into four domains: physical health, psychological health, social relationships, and environment.

Each question is scored on a Likert scale ranging from 1 (very poor) to 5 (very good), with higher scores indicating better quality of life. Demonstrates good reliability with Cronbach's α and split-half reliability of 0.92 and 0.93, respectively. Section 6 Data Processing and Statistical Analysis

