After data collection, the collected data will be coded, documented, and analyzed using the Statistical Package for the Social Sciences (SPSS) 19.0 Chinese version software. Both descriptive and inferential statistics will be employed. A significance level of p < .05 will be used to determine statistical significance.

1. Descriptive Statistics:

Categorical variables of demographic data for both experimental and control groups will be presented as percentages, while continuous variables will be described using means and standard deviations.

2. Inferential Statistics:

(a) Independent t-test or Mann-Whitney U test:

Analyze the differences between the experimental and control groups in variables such as balance function, muscle strength, flexibility, cardiovascular capacity, and quality of life befor intervention. A Shapiro-Wilk test will be conducted to check for normal distribution. If the data is normally distributed, an independent t-test will be used; otherwise, the Mann-Whitney U test will be employed.

(b) Chi-Squared Test:

Analyze the homogeneity of basic demographic characteristics (age, gender, education level, marital status), exercise habits, duration of each exercise session, and experience of falling in the past year between the two groups.

(c) Dependent Samples t-test or Wilcoxon Signed Rank Test: Analyze the differences in variables such as balance function, muscle strength, flexibility, cardiovascular capacity, and quality of life within each group 之前 and after the intervention. A Shapiro-Wilk test will be conducted to check for normal distribution. If the data is normally distributed, a dependent samples t-test will be used; otherwise, the Wilcoxon signed rank test will be employed.

(d) ANCOVA Analysis using Intention-to-Treat Analysis:

ANCOVA will be employed to compare the post-test scores between the experimental and control groups while controlling for pre-test scores. This analysis will utilize intention-to-treat principles.

[figure not shown]

Figure 8. Flowchart of the application of virtual reality interactive games

to the lower limb balance of community elders

Research Results

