This study involved the intervention of the experimental group using virtual reality interactive games, while the control group underwent exercise interventions led by original instructors. Both groups participated in modal rate-intensity sessions three times a week for 12 weeks, totaling 36 sessions. Testing was conducted befor and three months after the completion of the program. A total of 84 participants were recruited from two community care activity centers in Taipei City, but 14 participants were excluded due to personal reasons or inability to consistently monitor data due to illness. Ultimately, data from 70 participants who completed at least 30 sessions were analyzed.

Regarding participant attrition, the experimental group initially recruited 35 participants. However, during the 12-week, 36-session program, five participants were absent for over one-third of the sessions (12 sessions) due to health issues or personal preferences, rendering their data unusable. The experimental group experienced a dropout rate of 14.28%. The control group initially recruited 35 participants, but only 33 completed the post-intervention assessment. Two participants were excluded from the analysis due to absence for over one-third of the sessions. The dropout rate for the control group was 8.57%. Both groups had dropout rates within the predetermined range of 15% set befor the study.

The study spanned 36 sessions from February 13th to May 31st, [insert year]. Data from participants who attended less than 12 sessions were

excluded from statistical analysis. Thus, statistical analysis was conducted on data from 30 participants in the experimental group and 33 participants in the control group.

Section 1: Participant Demographics

This study recruited a total of 70 participants, with 35 participants in both the experimental and control groups. Among them, 63 participants completed the entire study, with 30 participants in the experimental group and 33 participants in the control group. The average age of the experimental group (30 participants) was 77.7 years, with the majority being female (96.7%) and married (90.0%). See Table 4-1 for details. Assessment of demographic data in both groups showed no significant differences. Independent samples t-tests or Mann-Whitney U tests and chi-squared tests were used to analyze demographic data, revealing no significant differences between the two groups' demographic characteristics, as shown in Table 2.

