The results of ANCOVA analysis (Table 6) revealed that the post-test scores of the experimental group were significantly higher than those of the control group in five assessment outcomes, including the 2-minute step test (p < 0.001), right chair sit and reach (p = 0.010), left chair sit and reach (p = 0.002), psychological quality of life (p = 0.033), and environmental quality of life (p = 0.048). Additionally, the differences in fitness (except for the 30-second chair stand test) and quality of life had effect sizes (partial eta squared) ranging from 0.011 to 0.267, indicating moderate to substantial intervention effects. These results suggest that the intervention in this study was more effective in improving the aforementioned fitness and quality of life compared to regular community activities.

	StatisticsF /(p)	effect size (partial eta
		squared)
BMI	0.195 (0.661)	0.003
30 seconds sit and stand	0.015 (0.904)	0.000
The seat body bends forward (right)	21.154 (<0.001)	0.267
The seat body bends forward (left)	7.091 (0.010)	0.109
Get up and walk Around at 2.4 meters	10.294 (0.002)	0.151
Physiological quality of life	0.667 (0.418)	0.011
Psychological quality of life	0.956 (0.332)	0.016
Quality of social life	4.766 (0.033)	0.076
Environment quality of life	1.405 (0.241)	0.024
The seat body bends forward (right)	4.080 (0.048)	0.066

Table 6Post-test comparison between the experimental group and the

control group

Note: This analysis uses ANCOVA to control the pretest scores and other significant influencing factors

in the pretest. The control variables include: age, education level, and pretest scores of each variable.

Section 3: Analysis and Comparison of Quality of Life Questionnaire

Upon statistical analysis of pre-test and post-test scores (Table 7), it was found that in the experimental group, there was a difference of 0.4points in the physical domain (p = 0.202), no difference in the psychological domain (p = 0.008), a difference of 0.2 points in the social relationships domain (p = 0.500), and no difference in the environmental domain (p = 0.500). In contrast, in the control group, there was a difference of 0.4 points in the physical domain (p = 0.325), no difference in the psychological domain (p = 1.000), and no difference in the social relationships and environmental domains. The results indicate a significant change in the quality of life in the physical domain for the experimental group.

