their willingness to engage in exercise but also enhanced their confidence and positive feelings by achieving game objectives. The game content was based on the recommendations of the American College of Sports Medicine for older adults engaging in regular physical activity, including strength training, balance exercises, flexibility exercises, and aerobic or endurance activities. In the game, older adults were required to stand with their feet stationary while moving their upper body in response to music and game elements such as coins and asteroids on the screen. They also had to raise their hands and perform stretching, bending, twisting, bending forward, arching backward, and leaning side to side to hit coins and asteroids. This not only increased the frequency and opportunities for upper body movement but also trained flexibility and balance. Considering the economic benefits and sustainability of exercise execution, the integration of the virtual airplane game created in this study with exercise programs provides a necessary measure for older adults in community centers to engage in regular health-promoting exercise and prevent or mitigate disability. Additionally, the system required participants to perform maximum body movements in all directions before each intervention session. The purpose was to record the maximum range of individual body movements and use them in training to achieve personalized and precise exercise interventions, thereby maximizing the benefits of improving physical fitness.

Section 2 The impact of virtual reality interactive game intervention on the physical fitness of the elderly

Although there is existing literature on interactive games for elderly training, most studies focus on residents of institutions such as day care centers, nursing homes, and rehabilitation centers (Hsieh, 2014; Chung, 2020; Du, 2021). Nowadays, community centers typically offer exercise programs led by sports professionals or instructors for elderly participants, including activities like Ba Duan Jin, chair yoga, step aerobics, fitness, resistance band exercises, and rehabilitation exercises (Chen et al., 2019; Jiang et al., 2020). However, these activities often involve older adults lining up facing the instructor and following instructions, which may not foster a positive and engaging group atmosphere.

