This study primarily utilized virtual reality interactive games for training. It employed a three-axis inertial sensor to monitor body angle changes during exercise. Older adults wore a waist protector embedded with sensors, which connected via Bluetooth to control a virtual aircraft in the game. Participants moved their bodies forward, backward, left, and right to collide with asteroids and coins in different directions, challenging their balance with varying levels of difficulty such as standing with feet parallel, slightly squatting with feet parallel, and standing with feet apart. implie m itionally, participants were required to raise their hands and perform stretching and bending movements in sync with body movements in the game. This not only increased upper body movement opportunities but also effectively maintained body balance, reducing the risk of falls during

the game. Researchers like Fang et al. (2016) found that using virtual reality Wii Fit games for training for more than 6 weeks can improve dynamic balance ability in older adults.

In this study, a custom-designed virtual airplane game allowed elderly participants in community center activities to effectively train balance and improve flexibility during exercise. By following game instructions for forward and backward movements, participants could earn scores and complete tasks successfully. After 36 sessions, significant improvements were observed in elderly participants who engaged in virtual reality interactive games, particularly in the 2-minute step test (p<0.001) and left and right chair stands (p<0.001, p=0.003). ANCOVA analysis revealed differences in physical fitness (except for the 30-second chair stand) and quality of life, with effect sizes (partial eta squared) ranging from 0.011 to 0.267, indicating moderate to substantial intervention effects. These findings demonstrate that the virtual reality intervention in this study outperformed conventional center-based activities in enhancing physical fitness and quality of life.

Section 3: The impact of virtual reality interactive game intervention on the quality of life of the elderly

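### The 2-minute step row of Table 5, which carries the trial's largest claimed effect, is internally inconsistent and should be reconciled with source records before its size is relied on

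*Combined protocol and SAP*

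**What the plan says.** Chapter 3, Section 5 describes stepping in place for two minutes, where "the number of times the knees are lifted to a specific height is counted". Section 6 plans paired tests within each arm and an ANCOVA of post-test adjusted for pre-test between arms: "A significance level of p < .05 will be used to determine statistical significance".

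The Research Results chapter analyses 63 people, "with 30 participants in the experimental group and 33 participants in the control group". Row labels in Tables 5 and 6 are shifted, but the pre-test values in Table 4 (96.0 ± 20.7 and 92.5 ± 25.4) identify the step row. Table 5 prints for that row:

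| Arm | Pre | Post | Change (pre minus post) | Statistic (p) |
|---|---|---|---|---|
| VR | 96.0 ± 20.7 | 121 ± 25.7 | -26.6 ± 31.2 | -4.67 (<0.001) |
| Control | 92.5 ± 25.4 | 98 ± 20.2 | -3.8 ± 15.0 | -1.47 (0.151) |

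In Table 6 the same outcome has F and p of "21.154 (<0.001") and partial eta squared 0.267. The Abstract lists it first among the significant results, and Chapter 5, Section 2 cites it first among the improvements: "particularly in the 2-minute step test (p<0.001").

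**The concern.** Two features of the row stand out. The mean change should equal the difference between the post-test and pre-test means if all three come from the same people, and in neither arm does it. Separately, the VR change SD is larger than either SD it derives from, so people's post-test counts were almost unrelated to their pre-test counts. That is unusual for a repeated fitness measure and unlike the rest of the table.

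This row supplies the smallest p-value and the upper end of the effect-size range that the Results and Discussion quote. If an entry is wrong, or the columns rest on different records, then the reported change, the paired test, and possibly the adjusted effect and its partial eta squared are wrong too. The documents do not comment on the discrepancy and describe no check of record linkage or counting.

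**Working it through.** Inputs are the Table 5 values above, with n = 30 and 33.

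**1. Reproduce the printed statistics.** Paired t = mean change / (SD of change / √n).
- VR: 26.6 / (31.2/√30) = 4.67, matching the printed value.
- Control: 3.8 / (15.0/√33) = 1.46 against 1.47 printed, within rounding.

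So 26.6 and 31.2 are the figures the analysis used with n = 30. The Table 5 footnote marks this row as a Wilcoxon test, but the printed number is a paired t.

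**2. Check the means.**
- VR: 121 - 96.0 = 25.0, against 26.6.
- Control: 98 - 92.5 = 5.5, against 3.8.

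The post-test means are printed as whole numbers. Allowing ±0.5 for them and ±0.05 for the pre-test means, the differences could be 24.45 to 25.55 in VR and 4.95 to 6.05 in controls. Neither range reaches the printed change.

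The gap can matter. If the control means and the SD of 15.0 were right, t would be 5.5 / (15.0/√33) = 2.11. That is beyond the two-sided 5% point of about 2.04 on 32 degrees of freedom, whereas the table reports p = 0.151.

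**3. Implied pre-post correlation.** r = (SDpre² + SDpost² - SDchange²) / (2 × SDpre × SDpost).
- VR: (428.49 + 660.49 - 973.44) / 1063.98 = 0.109; rounding range 0.102 to 0.115; 95% CI -0.26 to 0.45.
- Control: (645.16 + 408.04 - 225.00) / 1026.16 = 0.807; rounding range 0.805 to 0.809; 95% CI 0.64 to 0.90.

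**4. Compare with the other fitness rows.** The formula is the same, and the arms are compared by Fisher's z = (atanh r_control - atanh r_VR) / √(1/27 + 1/30).

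| Test | VR r | Control r | z |
|---|---|---|---|
| Chair stand | 0.76 | 0.96 | 3.4 |
| 2-minute step | 0.11 | 0.81 | 3.8 |
| Sit-and-reach, right | 0.72 | 0.97 | 4.7 |
| Sit-and-reach, left | 0.71 | 0.99 | 7.5 |
| Up-and-go | 0.49 | 0.98 | 6.8 |

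The step test has the lowest correlation in both arms. The gap between arms is not peculiar to it: three other rows show a larger z.

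**5. Does the effect depend on the pairing?**
- Post-test means only: (121 - 98) / √(25.7²/30 + 20.2²/33) = 23 / 5.86 = 3.92, Welch p = 0.0002.
- ANCOVA rebuilt from the summaries, with pre-test as the only covariate and VR r = 0.11: adjusted difference 21.4 (SE 5.2), F = 16.9, p = 0.0001.
- The same means and SDs with VR r set to 0.5, 0.7 or 0.8: F = 21.4, 26.6 or 31.1.

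The published F of 21.154 also adjusts for age and education, so the rebuilt F is not expected to match it.

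**The case against.** A reader might infer that the step-test effect is a record-matching or counting artefact and should not be claimed. The documents do not support that, for four reasons.

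- Linking VR pre-tests to the wrong post-tests would leave both means and the post-test contrast unchanged. It would inflate the change SD and weaken the tests, so correcting it would strengthen the result (step 5).
- A uniform change in counting, such as a fixed number of extra lifts or one knee against both, could shift the means but would not lower a correlation. Only counting that varied from person to person could do both, and nothing in the documents indicates it. Chapter 3, Section 5 does not say whether one or both knees count, but that applies to both arms.
- Correlations are lower in VR than in controls in every fitness row. More varied response in the VR arm, on a test that repeats less well, is a plausible reading. Within the VR arm, 0.11 is not clearly below the 0.49 for up-and-go (z = 1.6, p = 0.11, treating the two as independent).
- The game's description, "older adults were required to stand with their feet stationary while moving their upper body", might make a stepping gain look surprising. But Chapter 3, Section 4 also gives every session warm-up and cool-down exercise, so this is weak evidence.

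It is also fair to say that r = 0.11 is only as good as its inputs, and step 2 shows that the row's inputs do not agree with one another. All of this stands, and it rules out any presumption about the direction of an error. It does not remove the mismatch in the means, which needs correcting whatever its cause.

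**Conclusion.** The point holds as a data-consistency problem. The step row cannot be wholly correct as printed: the changes are off by 1.6 lifts in VR (26.6 - 25.0) and 1.7 in controls (5.5 - 3.8), both beyond rounding. The VR SDs imply r of about 0.11, on the assumption that all three come from the same 30 people. That is low against controls (0.81) and against the other VR fitness tests (0.49 to 0.76), but it could reflect uneven response.

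The evidence does not show that the effect is absent or overstated. Taking the printed post-test means and SDs at face value, the arms differ at p = 0.0002 without any pairing. What remains open is the size of the effect, including the mean change and the partial eta squared of 0.267. A corrected figure could move either way.

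**What to change.** Check the roughly 63 paired step-test records against the data file: participant ID, visit, and the same counting rule for every participant at both visits. Correct the means, changes and SDs, and state in Table 5 how many people each column uses. Re-run this row of Tables 5 and 6, and carry the corrected effect size into the Abstract, the Results and Chapter 5. Add to Chapter 3, Section 5 whether one or both knees are counted. If the records cannot be reconciled, keep the result but flag the size of the step-test effect as unverified.

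The cost is a small amount of checking and one re-run row. The downside is that the headline fitness figure may change in either direction.
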